## **5.7 Diet/Activity/Other Considerations**

### 5.7.1 Diet

Subjects should maintain a normal diet unless modifications are required to manage an AE such as diarrhea, nausea or vomiting.

### 5.7.2 Contraception

Pembrolizumab may have adverse effects on a fetus in utero. Furthermore, it is not known if pembrolizumab has transient adverse effects on the composition of sperm.

For this trial, male subjects will be considered to be of non-reproductive potential if they have azoospermia (whether due to having had a vasectomy or due to an underlying medical condition).

Female subjects will be considered of non-reproductive potential if they are either:

(1) postmenopausal (defined as at least 12 months with no menses without an alternative medical cause; in women < 45 years of age a high follicle stimulating hormone (FSH) level in the postmenopausal range may be used to confirm a post-menopausal state in women not using hormonal contraception or hormonal replacement therapy. In the absence of 12 months of amenorrhea, a single FSH measurement is insufficient.);

OR

(2) have had a hysterectomy and/or bilateral oophorectomy, bilateral salpingectomy or bilateral tubal ligation/occlusion, at least 6 weeks prior to screening;

OR

(3) has a congenital or acquired condition that prevents childbearing.

Female and male subjects of reproductive potential must agree to avoid becoming pregnant or impregnating a partner, respectively, while receiving study drug and for 120 days after the last dose of study drug by complying with one of the following:

(1) practice abstinence† from heterosexual activity; OR

(2) use (or have their partner use) acceptable contraception during heterosexual activity.

Acceptable methods of contraception are‡:

Single method (one of the following is acceptable):

- intrauterine device (IUD)
- vasectomy of a female subject's male partner
- contraceptive rod implanted into the skin

Combination method (requires use of two of the following):

- diaphragm with spermicide (cannot be used in conjunction with cervical cap/spermicide)
- cervical cap with spermicide (nulliparous women only)
- contraceptive sponge (nulliparous women only)

- male condom or female condom (cannot be used together)
- hormonal contraceptive: oral contraceptive pill (estrogen/progestin pill or progestin-only pill), contraceptive skin patch, vaginal contraceptive ring, or subcutaneous contraceptive injection

†Abstinence (relative to heterosexual activity) can be used as the sole method of contraception if it is consistently employed as the subject's preferred and usual lifestyle and if considered acceptable by local regulatory agencies and ERCs/IRBs. Periodic abstinence (e.g., calendar, ovulation, sympto-thermal, post-ovulation methods, etc.) and withdrawal are not acceptable methods of contraception.

‡If a contraceptive method listed above is restricted by local regulations/guidelines, then it does not qualify as an acceptable method of contraception for subjects participating at sites in this country/region.

Subjects should be informed that taking the study medication may involve unknown risks to the fetus (unborn baby) if pregnancy were to occur during the study. In order to participate in the study subjects of childbearing potential must adhere to the contraception requirement (described above) from the day of study medication initiation (or 14 days prior to the initiation of study medication for oral contraception) throughout the study period up to 120 days after the last dose of trial therapy. If there is any question that a subject of childbearing potential will not reliably comply with the requirements for contraception, that subject should not be entered into the study.

#### 5.7.3 Use in Pregnancy

If a subject inadvertently becomes pregnant while on treatment with pembrolizumab, the subject will immediately be removed from the study. The site will contact the subject at least monthly and document the subject's status until the pregnancy has been completed or terminated. The outcome of the pregnancy will be reported to the Principal Investigator and to Merck without delay and within 24 hours to the Principal Investigator and within 2 working days to Merck if the outcome is a serious adverse experience (e.g., death, abortion, congenital anomaly, or other disabling or life-threatening complication to the mother or newborn).

The study investigator will make every effort to obtain permission to follow the outcome of the pregnancy and report the condition of the fetus or newborn to the Principal Investigator. If a male subject impregnates his female partner the study personnel at the site must be informed immediately and the pregnancy reported to the Principal Investigator and to Merck and followed as described above and in Section 7.2.2.

#### 5.7.4 Use in Nursing Women

It is unknown whether pembrolizumab is excreted in human milk. Since many drugs are excreted in human milk, and because of the potential for serious adverse reactions in the nursing infant, subjects who are breast-feeding are not eligible for enrollment.

### **5.8 Subject Withdrawal/Discontinuation Criteria**

Subjects may withdraw consent at any time for any reason or be dropped from the trial at the discretion of the investigator should any untoward effect occur. In addition, a subject may be withdrawn by the investigator or the Principal Investigator if enrollment into the trial is inappropriate, the trial plan is violated, or for administrative and/or other safety reasons. Specific details regarding discontinuation or withdrawal are provided in Section 7.1.4 – Other Procedures.

A subject must be discontinued from the trial for any of the following reasons:

- 5.9.5 The subject or legal representative (such as a parent or legal guardian) withdraws consent.
- 5.9.6 Confirmed radiographic disease progression
- 5.9.7 Intercurrent illness that prevents further administration of treatment per protocol
- 5.9.8 Investigator's decision to withdraw the subject
- 5.9.9 The subject has a confirmed positive serum pregnancy test
- 5.9.10 Noncompliance with trial treatment or procedure requirements
- 5.9.11 The subject is lost to follow-up
- 5.9.12 Administrative reasons

The End of Treatment and Follow-up visit procedures are listed in Section 6. After the end of treatment, each subject will be followed for 30 days for adverse event monitoring (serious adverse events will be collected for 90 days after the end of treatment). Subjects who discontinue for reasons other than progressive disease will have post-treatment follow-up for disease status until disease progression, initiating a non-study cancer treatment, withdrawing consent or becoming lost to follow-up. After documented disease progression each subject will be followed by telephone for overall survival until death, withdrawal of consent, or the end of the study, whichever occurs first.

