### 2.2 Trial Diagram

Two consecutive run-in cohorts will be treated establishing the safety of neoadjuvant pembrolizumab and pembrolizumab-SRT delivered in the preoperative window. An expansion cohort will include a larger number of patients who will be treated with pembrolizumab alone or be randomized between the two arms.

**Cohort 1:** 6 patients. The patients will undergo 2 cycles of pembrolizumab prior to surgery. Surgery will occur no later than 6 weeks following the last dose of pembrolizumab.

If  $\leq 33\%$  of patients experience grade 3 immune-related toxicity attributable to study interventions (as determined within 30 days of date of surgery), or  $\leq 1$  patient progresses to unresectability over the course of study treatment, proceed to Cohort 2.

If  $>33\%$  of patients experience grade 3 immune-related toxicity attributable to study interventions (as determined within 30 days of date of surgery), or  $> 1$  patient progresses to unresectability over the course of study treatment, the study will terminate.

**Cohort 2:** 6 patients. The patients will undergo 2 cycles of pembrolizumab then within the week (7 days  $\pm$  3 days) following administration of the second cycle, a single fraction of SRT (12 Gy) will be delivered to 50% of the primary tumor only. Definitive surgical resection will occur

[figure not shown]
no later than 6 weeks following the last dose of pembrolizumab.

If  $\leq 33\%$  of patients experience grade 3 immune-related toxicity attributable to study interventions (as determined within 30 days of date of surgery), or  $\leq 1$  patient progresses to unresectability over the course of study treatment, proceed to Expansion Cohort (randomization between parameters of Cohort 1 and Cohort 2, e.g. randomization between preoperative pembrolizumab versus pembrolizumab and SRT).

If >33% of patients in Cohort 2 experience grade 3 immune-related toxicity attributable to study interventions (as determined within 30 days of date of surgery), or > 1 patient progresses to unresectability over the course of study treatment, then proceed to Expansion Cohort (parameters only of Cohort 1, e.g. preoperative pembrolizumab alone).

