### **5.9 Subject Replacement Strategy**

Patients who drop out before starting pembrolizumab will be replaced. In addition, patients who come off study before completing surgery without grade  $\geq 3$  toxicity will be replaced. The frequency of each of these events will be reported and reasons for replacement reviewed.

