##### *6.2.5.2 Post-treatment samples:*

Patients will undergo surgical resection of their primary tumor and associated lymph nodes. Patients in cohort 1 will have received pembrolizumab alone prior to resection, whereas patients in cohort 2 will have received pembrolizumab and radiation to half of the primary tumor.

In all cases, post-treatment excisional samples should be first taken from the primary tumor tissue that was treated with pembrolizumab only (medially oriented half of tumor). The portion of tumor which received radiation is the lateral aspect of the tumor relative to the patient.

Therefore, mandated post-treatment tissue samples should always be removed from the medial aspect of the tumor.

If it is feasible and specimen collection will not interfere with the patient's clinical care, tissue samples should also be collected from the radiated portion of the tumor (lateral aspect). These tumor samples should be labeled so that their orientation (medial vs lateral) is clear.

Samples from clinically involved lymph nodes are requested if feasible and if collection will not interfere with the patient's clinical care. These samples should be labeled by the designated nodal station.

Sample collection, storage and shipment instructions for post-treatment tissue samples are provided in the Laboratory Manual.

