### 6.2.10 Treatment Period

Treatment will initiate with the first dose of pembrolizumab. A second dose of pembrolizumab will be delivered 3 weeks later, +/- 3 days.

If the patient is scheduled to receive SRT on the protocol, the day of radiation delivery will be no later than 7 days following the date anticipated for administration of the second cycle of pembrolizumab, +/- 3 days. If the second cycle is not given, then SRT should not be given.

Surgical resection, if the patient is medically and physically able to undergo the procedure, should be delivered no later than 6 weeks (42 days +/- 3 days) after the last dose of pembrolizumab.

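### Section 5.8 takes still-resectable patients off the trial for progression or dose-limiting illness, so entry to the paired-specimen primary endpoint can depend on a post-treatment event

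*Combined protocol and SAP*

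**What the plan says.** Section 5.8 opens its list with "A subject must be discontinued from the trial for any of the following reasons". Two entries matter here: "Confirmed radiographic disease progression" and "Intercurrent illness that prevents further administration of treatment per protocol". Neither mentions resectability, and the object of the sentence is the trial, not the study drug. The section then says: "After documented disease progression each subject will be followed by telephone for overall survival until death".

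Section 5.9 replaces "patients who come off study before completing surgery without grade" 3 or higher toxicity, without setting progression apart. Its next sentence requires the frequency of, and reasons for, replacement to be reported and reviewed.

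Other sections point towards operating and sampling:

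- Section 6.2.10: "Surgical resection, if the patient is medically and physically able to undergo the procedure, should be delivered no later than 6 weeks". The condition is fitness, not absence of progression.
- Section 6.2.5.2: "mandated post-treatment tissue samples should always be removed from the medial aspect of the tumor".
- Section 2.2, SRT footnote: a patient who misses the second cycle because of discontinuation gets no SRT but goes on to surgery once the surgeon considers it safe.
- Section 2.2, run-in rules: the progression count is of cases where a "patient progresses to unresectability over the course of study treatment".

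The primary objective (3.1) needs a biopsy and a resection specimen from the same patient. Section 7.2 names one exclusion from the primary endpoint, an inadequate baseline core biopsy, and has no rule for a treated patient without a resection specimen.

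**The concern.** A patient has started pembrolizumab, is scanned off-schedule, shows confirmed progression and can still be resected. Under the literal text of 5.8 that patient leaves the trial. If there has been no grade 3 or higher toxicity, 5.9 brings in another patient. The first contributes no on-trial resection specimen, and the endpoint is measured in the replacement. Under 6.2.10 and 6.2.5.2 the same patient is operated on, sampled and counted. The same split arises for an illness that blocks the second dose: 5.8 removes the patient, while the 2.2 footnote sends to surgery a patient whose second cycle is not given.

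Who is affected by the progression rule depends on who is scanned. The flow chart (6.1) schedules no tumour imaging between screening and surgery, and its footnote h leaves imaging during treatment to the investigator. The trial is open label (5.2.3). The number affected may be small, but the test rests on about 26 patients, so the denominator should be settled before the specimens are read.

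**Working it through.** **Inputs.** From 7.2: null rate 15%, alternative 40%, 26 evaluable patients, exact binomial test, one-sided 5%, stated power 90%. The documents do not give the number of treated, resectable patients removed before surgery. The counts m = 1, 2, 3 per 26 kept are assumptions.

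**Step 1. The plan's own figure.** The smallest cut-off with P(X ≥ c | 26, 0.15) ≤ 0.05 is c = 8:

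- P(X ≥ 7 | 26, 0.15) = 0.083, too large.
- P(X ≥ 8 | 26, 0.15) = 0.032.
- P(X ≥ 8 | 26, 0.40) = 0.878.

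Power is 87.8%, against 90% stated. With 27 patients (40 × 2/3 = 26.7, rounded up) the same cut-off gives 90.5%. This small gap is a separate matter and does not affect what follows.

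**Step 2. Put removed patients back into an observed result as non-responders.** The responder count stays fixed and n rises by the number removed. The p-value is P(X ≥ x | n, 0.15).

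| Observed | Removed | Result | p |
|---|---|---|---|
| 8/26 | 0 | 8/26 | 0.032 |
| 8/26 | 1 | 8/27 | 0.040 |
| 8/26 | 2 | 8/28 | 0.049 |
| 8/26 | 3 | 8/29 | 0.059 |
| 9/26 | 0 | 9/26 | 0.011 |
| 9/26 | 7 | 9/33 | 0.0495 |
| 9/26 | 8 | 9/34 | 0.059 |

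**Step 3. Operating characteristics at the fixed rule of 8 or more of 26.** Let q = m/(26 + m) be the share removed.

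- All removed are non-responders and the true all-treated rate is 15%: the rate among those kept is 0.15/(1 − q).
- All removed are responders and the true all-treated rate is 40%: the rate among those kept is (0.40 − q)/(1 − q).

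| m | q | Rate kept (non-responders removed) | Type I error | Rate kept (responders removed) | Power |
|---|---|---|---|---|---|
| 0 | 0 | 0.1500 | 3.2% | 0.4000 | 87.8% |
| 1 | 0.0370 | 0.1558 | 3.9% | 0.3769 | 82.3% |
| 2 | 0.0714 | 0.1615 | 4.7% | 0.3538 | 75.3% |
| 3 | 0.1034 | 0.1673 | 5.7% | 0.3308 | 66.9% |

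Both columns are extremes. A mix lies between them, and if removed patients respond at the same rate as the rest, type I error and power are unchanged.

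**Step 4. Behaviour of the proposed sensitivity analysis.** With 26 observed pairs plus k treated patients with no resection specimen, all counted as non-responders, the test uses n = 26 + k.

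- k = 1 or 2: P(X ≥ 8 | 28, 0.15) = 0.049, so the cut-off stays at 8 and power is 87.8%.
- k = 3 to 7: P(X ≥ 8 | 29, 0.15) = 0.059 and P(X ≥ 9 | 33, 0.15) = 0.0495, so the cut-off is 9. Power is P(X ≥ 9 | 26, 0.40) = 77.4%.

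**The case against.** The best defence is that 5.8 is general discontinuation language and the trial-specific text governs. The 2.2 footnote shows that discontinuation does not in itself end the path to surgery. Section 6.2.10 ties surgery to fitness, and 6.2.5.2 calls for samples in all cases. Patients discontinued under 5.8 are still followed for adverse events, disease status or survival, so discontinuation there is not complete removal. This stands as evidence of likely intent. It does not cancel a mandatory rule that names the trial and makes no exception; if the intent is that resectable patients are operated on and counted, 5.8 contradicts it.

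The defence is also right that few patients would qualify. A patient must be scanned off-schedule, have progression confirmed in a short preoperative window, remain resectable, have adequate baseline tissue and, to be replaced, be free of grade 3 or higher toxicity. Patients who become unresectable have no resection specimen whatever 5.8 says. One or two removals keep type I error below 5% even in the worst case. Reporting replacements under 5.9 would let a reader redo Step 2, although it does not fix the denominator in advance.

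A reader might infer that the protocol forbids surgery or tissue collection after progression. It does not: nothing in 5.8 says so. A reader might also infer that the primary result will be biased in favour of treatment. The documents do not link progression to CD3+ change, so neither direction nor size can be derived. Nor is it a fault that the endpoint depends on surgery, since any paired biopsy-resection endpoint does. The narrower fault is that patients who could be resected may be taken out and replaced.

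**Conclusion.** The point holds as a conflict between stated rules with a limited consequence. Sections 5.8 and 5.9, applied as written, remove and replace treated, resectable patients because of an event after treatment start. The 2.2 footnote and 6.2.10 would keep them, and no text says expressly which prevails.

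Under the assumption that all removed patients are non-responders, three per 26 kept is the smallest number that takes type I error past 5% or overturns a borderline 8/26. A result of 9/26 would need eight. If all were responders, even one would lower power to 82.3%. The assumed counts are not estimates. The concern deserves correction because the edit is cheap and the choice should not be open once CD3+ results are known. It does not show that the trial is invalid or its error rate inflated. Confidence is medium: the text is clear, but the number affected is unknown and probably small.

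**What to change.** **Section 5.8.** Make confirmed radiographic progression, and intercurrent illness that prevents further dosing, reasons to stop study treatment rather than to leave the trial. State that any treated patient who is resected stays on study, provides the mandated specimen and counts in the primary endpoint if baseline tissue is adequate. Such a patient has not left before surgery, so 5.9 needs no extra replacement clause. Leave the other reasons in 5.8 as they are. Whether and when to operate stays with the treating surgeon.

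**Section 7.2.** Add a sensitivity analysis that counts as non-responders all treated patients with adequate baseline tissue but no resection specimen. After the change to 5.8 these will mainly be unresectable or withdrawn patients, including those replaced under 5.9. The primary test stays as planned.

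**Cost.** A short amendment and no new procedure, since the tissue comes from a resection the patient has anyway. The responder rate may be slightly lower, and some counted patients will have had one cycle or no SRT. The sensitivity analysis is conservative: its cut-off stays at 8 with one or two missing specimens and rises to 9, with 77.4% power, for three to seven.

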## 2.0 TRIAL DESIGN

### 2.1 Trial Design

This is a randomized single-institution, phase II, open-label clinical trial of neoadjuvant pembrolizumab with or without low-dose stereotactic radiation therapy (SRT) in stage I- IIIA non-small lung cancer (NSCLC) patients who are planned to undergo surgical resection of their lung cancer.

Two consecutive run-in cohorts will administer pembrolizumab or pembrolizumab with SRT of 12 Gy to the lateral aspect of the primary tumor. Patients will receive pembrolizumab for 2 cycles prior to surgery or SRT and surgery. Surgical resection of all involved areas of tumor will occur within 6 weeks of the last administration of pembrolizumab. It should be noted that in almost all cases, surgery is expected to occur very expeditiously, within a much shorter window and 6 weeks would represent only the greatest allowable amount of delay.

If during the run-in, only the pembrolizumab-alone cohort meets pre-specified safety parameters, subsequently enrolled patients will enter a larger expansion cohort, with treatment given according to that cohort only. If during the run-in both cohorts meet pre-specified safety parameters, subsequently enrolled patients will enter the expansion cohort and be randomized between preoperative pembrolizumab versus pembrolizumab with SRT of 12 Gy.

Patients will be followed every 12 weeks for 1 year for disease status and survival.

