#### 3.2 Secondary Objectives & Hypotheses

(1) **Objective:** To assess the safety of preoperative pembrolizumab +/- SRT when combined with surgery;

**Hypothesis:** In patients scheduled for NSCLC resection, pembrolizumab, or pembrolizumab + SRT, given in the preoperative window, will meet safety criteria described by the protocol;

(2) **Objective:** To record the toxicity of preoperative pembrolizumab +/- SRT when combined with surgery, according to CTCAE v. 4, including immune-related adverse events (AEs);

**Hypothesis:** In patients scheduled for NSCLC resection, pembrolizumab, or pembrolizumab + SRT, given in the preoperative window, will result in acceptable short-term and perioperative toxicity;

(3) **Objective:** To determine the 1-year overall survival rate resulting from preoperative pembrolizumab +/- SRT when combined with surgery;

**Hypothesis:** In patients scheduled for NSCLC resection, pembrolizumab + SRT given in the preoperative window will result in a higher 1-year survival rate than pembrolizumab alone;

(4) **Objective:** To determine the 1-year relapse free survival rate resulting from preoperative pembrolizumab +/- SRT when combined with surgery;

**Hypothesis:** In patients scheduled for NSCLC resection, pembrolizumab + SRT given in the preoperative window will result in a higher 1-year relapse free survival rate than pembrolizumab alone;

(5) **Objective:** To determine the 1-year rate of distant metastases resulting from preoperative pembrolizumab +/- SRT when combined with surgery;

**Hypothesis:** In patients scheduled for NSCLC resection, pembrolizumab + SRT given in the preoperative window will result in a lower 1-year distant metastasis rate than pembrolizumab alone;

(6) **Objective:** To assess quality of life associated with preoperative pembrolizumab +/- SRT when combined with surgery;

**Hypothesis:** In patients scheduled for NSCLC resection, pembrolizumab, or pembrolizumab + SRT, given in the preoperative window, will result in acceptable short-term and perioperative quality of life;

(7) **Objective:** To determine the rate of unresectability that results from a program of preoperative pembrolizumab +/- SRT to be followed by a planned surgery;

**Hypothesis:** In patients scheduled for NSCLC resection, either pembrolizumab or pembrolizumab + SRT given in the preoperative window will both result in <15% overall rate of unresectability following the preoperative program;

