### 6.2.11 Post-Treatment/Safety Follow-Up Visits

After the date of surgery, patients will return for clinical and laboratory assessments at 30 days (first follow-up visit), 90 days, 180 days, and 360 days (+/- 14 days) after the date of surgery. These assessments are required but imaging studies are to be ordered at the discretion of the investigator or a qualified designee.

All AEs that occur prior to the Safety Follow-Up Visit should be recorded. Subjects with an AE of Grade > 1 will be followed until the resolution of the AE to Grade 0-1 or until the beginning of a new anti-neoplastic therapy, whichever occurs first. SAEs that occur within 90 days of the end of treatment or before initiation of a new anti-cancer treatment should also be followed and recorded.

Every effort should be made to collect information regarding disease status until the start of new anti-neoplastic therapy, disease progression, death, end of the study. Information regarding post-study anti-neoplastic treatment will be collected if new treatment is initiated.

Correlative blood samples will be collected at each follow-up visit. Details are provided in Section 6.0 – Trial Flow Chart

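### Sections 5.8, 6.2.1.4.3 and 6.2.11 stop disease-status collection at first progression or new anti-cancer therapy, against one year in Section 2.1, so an any-time 1-year distant-metastasis rate would be biased downward

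*Combined protocol and SAP*

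**What the plan says.** **The endpoint.** Section 3.2, objective 5: "To determine the 1-year rate of distant metastases resulting from preoperative pembrolizumab +/- SRT when combined with surgery". Its hypothesis is that the SRT arm "will result in a lower 1-year distant metastasis rate than pembrolizumab alone". Relapse-free survival is a separate objective (objective 4). Section 7 gives no definition or analysis for either.

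**Rules that stop disease follow-up.**
- Section 5.8 lists "Confirmed radiographic disease progression" among the mandatory reasons for discontinuing a subject, with no split into local, regional and distant. Afterwards: "After documented disease progression each subject will be followed by telephone for overall survival until death, withdrawal of consent, or the end of the study".
- Section 5.8 adds that subjects who discontinue for other reasons "will have post-treatment follow-up for disease status until disease progression, initiating a non-study cancer treatment, withdrawing consent or becoming lost to follow-up".
- Section 6.2.11 asks for every effort to "collect information regarding disease status until the start of new anti-neoplastic therapy, disease progression, death, end of the study".
- Section 6.2.1.4.3 moves a subject to survival follow-up once new anti-cancer therapy has begun.

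**Text pointing the other way.** Section 2.1: "Patients will be followed every 12 weeks for 1 year for disease status and survival". Section 6.2.11 schedules visits at 30, 90, 180 and 360 days after surgery, and the flow chart in Section 6.1 lists a chest CT at day 360 or when clinically indicated. Neither makes an exception for patients who have progressed.

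**The concern.** Stopping at the first progression is enough for relapse-free survival, because the first event closes that endpoint. It is not enough for the rate of one type of failure when another type can come first. Take a patient with a mediastinal relapse at month 4 and a brain metastasis at month 8. Sections 5.8 and 6.2.11 give no one the task of recording the second event, and the patient may be counted as free of distant metastasis at one year. What could then be reported is distant metastasis as first failure, under the name of a 1-year distant-metastasis rate.

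The new-therapy stop has a similar effect. A patient treated for a local relapse meets both stopping rules, so lifting only the progression rule would not bring that patient back into disease follow-up.

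**Working it through.** **Step 1. The passages side by side, for the patient above (relapse at month 4, metastasis at month 8).**
- Section 2.1: still under disease follow-up at month 8, so the metastasis is within scope.
- Section 5.8: discontinued at month 4, then telephoned about survival.
- Section 6.2.6: on early discontinuation, the final-visit activities are done at that time. This points to month 4 rather than day 360.
- Section 6.2.11: disease-status collection ends at month 4, although the same section schedules a day-360 visit.
- Section 6.2.1.4.3: if the relapse is treated, survival follow-up only.

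The year of follow-up in Section 2.1 and the stops in the other sections cannot all be applied to this patient.

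**Step 2. Is there a stated figure to reproduce?** No. Section 7.2 powers only the CD3+ endpoint. The documents give no expected rate of relapse or distant metastasis.

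**Step 3. Weight of one missed case.** The two run-in cohorts have 6 patients each and the expansion cohort 28 (Section 2.2). Assuming equal allocation in the blocks of 4 (Section 5.3), 28 / 2 = 14 randomised per arm and 6 + 14 = 20 per treatment.
- 1/20 = 5.0 percentage points.
- 1/14 = 7.1 percentage points.

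**Step 4. Illustrative number of missed cases.** Every rate here is an assumption.

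Missed = N × (1-year relapse rate) × (share local or regional first) × (share of those with distant spread within the year).
- Low: 40 × 0.15 × 0.25 × 0.20 = 0.3 patients.
- High: 40 × 0.30 × 0.40 × 0.50 = 2.4 patients.

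**Step 5. Sensitivity to a wider range.** Let D be the rate of distant metastasis as first event, L the rate of local or regional progression first, and q the share of those with distant spread by one year. The rate captured is D; the any-time rate is D + L × q.
- L = 5%, q = 20%: 0.05 × 0.20 = 1 point, or 0.4 of 40 patients.
- L = 15%, q = 60%: 0.15 × 0.60 = 9 points, or 3.6 of 40 patients.
- With D = 10%, the any-time rate is 11% to 19% against 10% captured. The relative undercount is 1/11 = 9% to 9/19 = 47%.
- If the endpoint is defined as first failure, the target is D itself and the undercount from this mechanism is 0.

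Steps 4 and 5 count a progressed patient as free of later metastasis. The plan does not say whether such a patient would instead be censored.

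**Step 6. The new-therapy stop.** Section 2.2 allows standard adjuvant therapy after surgery, and no section says whether it counts as new or non-study cancer therapy. If it does, disease follow-up could end before any relapse. With an assumed true rate of 15%, and 20% to 60% of patients starting such therapy before the event independently of risk, the rate captured is 0.15 × 0.80 = 12% down to 0.15 × 0.40 = 6%. Relapse-free survival would be affected as well.

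**The case against.** A reader might infer that trial participation ends at progression and that a later distant metastasis is never recorded. The documents do not support that. Section 5.8 itself continues survival contact, and parts of its list concern further treatment, so discontinuation may be meant as coming off treatment. Section 2.1 promises a year of disease follow-up to all patients. Section 6.2.11 calls the visit assessments to day 360 required, and the flow chart lists survival status and post-study therapy status in follow-up. A metastasis could well be noted at one of these contacts.

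It is also fair to say that an undercount presupposes an any-time definition the plan does not give. Finally, Sections 4.3.4 and 4.4 describe the 1-year clinical outcomes as exploratory, with no power or test attached, so no planned decision turns on this rate.

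These points limit the finding to a conflict and a conditional bias, but they do not remove it. Section 6.2.11 contains both the visit schedule and the stop, and Section 6.2.6 brings the final-visit activities forward for a discontinued patient. Nothing names first failure as the endpoint, and objective 4 already covers the first event. A site following the specific follow-up text would have no instruction to capture the later metastasis.

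**Conclusion.** The point holds as an internal conflict with a conditional consequence. If objective 5 is an any-time rate, following Sections 5.8, 6.2.1.4.3 and 6.2.11 biases it downward. The size cannot be derived from the documents: 0.3 to 2.4 of 40 patients under one set of assumed rates and 0.4 to 3.6 under a wider set, so possibly less than one patient. Each missed case still moves an arm by 5 to 7 points.

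Two further inferences are tempting and should not be drawn.
- **That the bias favours a particular arm.** The arm with fewer local or regional relapses would be observed longer for distant disease. This matters only if SRT changes those relapses, and nothing in the documents allows it to be quantified.
- **That a patient with radiographic progression before surgery who remains resectable is lost to the primary endpoint.** Section 7.2 excludes only patients whose core biopsy proves inadequate. Imaging during treatment is discretionary, so few such cases would surface. Section 5.8 would discontinue this patient, Section 5.9 might replace the patient, and Section 2.2 counts only unresectability. The documents leave the handling open; they do not say the specimen is excluded.

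**What to change.** 1. Define objective 5 as first distant metastasis at any time up to day 360 after surgery, regardless of an earlier local or regional relapse. State how death is handled and the time origin for patients who never reach surgery.
2. In Sections 5.8, 6.2.1.4.3 and 6.2.11, separate *off study treatment* from *off trial*. Keep recording the date and site of first distant metastasis to day 360, both after progression and after new anti-cancer therapy, at the existing survival contact and from available routine-care records. State that standard adjuvant therapy does not end this collection.
3. Align these sections, and Section 6.2.6, with the one-year follow-up in Section 2.1.
4. Separately, reconcile Sections 5.8 and 5.9 with Section 2.2 for a patient with radiographic progression before surgery who remains resectable, and say whether that patient's specimen and follow-up data are kept for analysis.

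**Cost.** Protocol wording, one CRF field and a small amount of added record follow-up. The record follow-up is new work, because no section now specifies chart review after progression. No scans or visits are added, so detection after progression would still depend on routine care.
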